## 7.6.1. Monitoring Adverse Events of Special Interest

### 7.6.1.1. Adjudicated Arthropathy

Adjudicated arthropathy is an umbrella term that encompasses the following conditions:

- Rapidly progressive OA type 1 and 2
- Subchondral insufficiency fractures
- Primary osteonecrosis

In addition, adjudicated arthropathies will be evaluated to determine if they meet the criteria for destructive arthropathy.

Potential events of adjudicated arthropathy will be monitored via clinical signs and symptoms of worsening joint pain (joint pain questionnaire), AE monitoring, and routine imaging.

Clinically significant worsening of joint pain during the course of this study is defined as worsening of pain in any joint despite treatment with analgesics (see Section 5.2), which is inconsistent with the normal progression of OA and that lasts at least 2 weeks (or less at the discretion of the investigator).

If a patient reports an increase in joint pain, as described above, then study drug administration will be withheld. Imaging of the affected joint will be performed, as well as any additional imaging deemed appropriate to understand the cause of the worsening pain (Section 6.3.4.8). The decision to perform imaging after patient reports of worsening joint pain will be documented in the respective CRF page. Images, along with any other radiographic evaluation, will be submitted to the Adjudication Committee for review (Section 3.4). The investigator may consider aspiration of synovial fluid for further analysis such as cell count and crystal analysis.

If routine imaging suggests one of the forms of adjudicated arthropathy, then study drug administration will be withheld. Any additional imaging deemed appropriate will be obtained. Images, along with any other radiographic evaluation, will be submitted to the Adjudication Committee for review (Section 3.4).

If the adjudication does not confirm the case as adjudicated arthropathy according to the adjudication criteria, study drug may be restarted.

Patients with findings that suggest adjudicated arthropathy will have their dosing terminated and will be referred for orthopedic consultation, and once confirmed by the adjudication committee, the case must be reported as an AESI (Section 7.3.3 and Section 7.4.3).

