### 9.5.3. Safety Analysis

The incidence rate is defined as the number of events divided by the duration of the overall observation period. The incidence rate will be summarized by treatment group along with 2-sided 95% confidence interval. The incidence rate differences and ratios between each fasinumab dose group and placebo will be computed and presented along with 2-sided 95% confidence intervals.

Change from baseline in joint space width of the index knee or hip will be summarized by treatment group. Time to event endpoints, such as time to JR decision, will be analyzed using the Kaplan-Meier approach.

For safety variables, the following observation periods are defined:

- The pretreatment period is defined as the time from signing the ICF to before the first dose of study drug
- The on-treatment period is defined as the day of the first dose of study drug to 4 weeks after the day of the last dose of SC study drug.
- The follow-up period is defined as from the end of the on-treatment period up to 24 weeks post the last dose of study drug (week 72).

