2.2. Sample Size and Power Considerations

Long Term Safety study

The sample size for this long-term safety study was selected according to regulatory requirements for sufficient patients with adequate treatment exposure. With approximately 1750 patients expected to be treated with placebo, a total of up to 7000 patients was planned to be randomized. This study will provide an adequate assessment of safety in patients with pain associated with OA. For example, based on Exact Binomial Testing, with approximately 5250 patients with pain

associated with OA exposed to fasinumab, if the observed incidence rate of is 1.0%, one can be 97.5% confident that the true incidence rate is not greater than 1.3% (Table 1).

Departures from planned sample sizes will be described in the CSR.

Table 1: Observed Incidence Rate (n/N) and 95% CI (Based on Exact Binomial Test) (%)

	2-sided 95% CI
Observed Incidence Rate	All fasinumab combined (N=5250)
0.5%	(0.32%, 0.72%)
1%	(0.74%, 1.30%)
2%	(1.64%, 2.42%)
3%	(2.56%, 3.51%)
4%	(3.49%, 4.57%)
5%	(4.42%, 5.61%)

Efficacy Sub-study

The sample size of the efficacy sub-study was selected to have a sufficient number of patients to allow treatment comparisons of primary efficacy endpoints. The effect size for WOMAC pain subscale score, WOMAC physical function subscale score and Patient Global Assessment were 0.46, 0.46, and 0.36, respectively, as observed in the phase 2 study R475-PN-1227. To maintain the overall significance level of 0.05, the sequential multiple test procedure as described in Section 5.6.1 is applied to the hypothesis tests for the primary and secondary endpoints.

Assuming a dropout rate of 15% at week 16, with 200 patients per treatment arm, there will be at least 96% power to detect an effect size of 0.46 for WOMAC pain and physical function subscale scores based on a 2-sided test at the 0.0167 significance level. This sample size will provide at least 82% power to detect an effect size of 0.36 for Patient Global Assessment score.

[figure not shown]

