4.5.1. Primary Safety Variables

The primary safety endpoint in the study is safety monitoring including AE incidence, SAE, incidence, AESI incidence, changes in safety lab analyses, and incidence of anti-fasimumab antibody formation from baseline to week 52 (treatment period 1 and 2) and to week 72 (end of follow-up period).

More specifically, this includes:

- Incidence of adjudicated arthropathy events
- Incidence of destructive arthropathy events
- Incidence of JR (All JRs and AESI JRs) events – including endpoint for all JRs by the telephone survey approximately 52 weeks after the last dose of study drug
- Incidence of peripheral neurosensory AESI events

- Incidence of sympathetic nervous system dysfunction AESI events
- AE incidence, SAE incidence, changes from baseline in safety laboratory analyses, and incidence of anti-fasimumab antibody formation
- Change from baseline in minimum joint space width of the index joint (knee, hip)
- Incidence of confirmed orthostatic hypotension from baseline

The raw incidence rate is defined as the number of events divided by the duration of the observation period and presented as number of events per 100 patient-years.

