5.1.7.1. Primary Safety Endpoints

Incidence rate ratio estimates and 2-sided 95% confidence interval will be computed using Generalized Estimating Equations with a log-linked Poisson model via the PROC GENMOD procedure if there are events in the placebo group. The model will specify the use of a Poisson probability distribution with an offset= log (patient-observation period days) and model terms for treatment-as-received and each randomization strata. The 95% confidence interval for the

estimates of the difference in incidence rates will be computed using the same model. If there is no event in the placebo group, incidence rate ratio will not be calculated and confidence intervals for the incidence rate difference will be computed using Wald method. The incidence rate estimates for each arm, the estimates of the incidence rate ratio and incidence rate difference between fasinumab and placebo will be provided with the corresponding 95% confidence interval.

AE and SAE incidence will be summarized by treatment group based on the SAF-LTS by treatment group and combined fasinumab group.

Continuous variables will be summarized by baseline and change from baseline to each scheduled assessment time with descriptive statistics based on the SAF-LTS by treatment group and combined fasinumab group.

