5.1.8. Exploratory Safety Endpoints

Other safety endpoints in the study are:

- The proportion of patients taking rescue medication, number of days on rescue medication, and weekly average usage of rescue medication
- The percent of patients using standard-of-care analgesic medication from week 16 to week 52
- Time to JR decision
- Survey of Autonomic Symptoms Scores:
 - number of patients reporting health symptoms for each symptom/health problem assessed at each scheduled visit
 - number of symptoms reported and total symptom impact score at each scheduled visit
- Time to AA, time to DA

The exploratory safety variables comparing incidence rate of each fasinumab dose group and placebo will be analyzed using the same method as the primary safety endpoints.

The exploratory safety variables comparing change from baseline scores of each fasinumab dose group and placebo will be analyzed using the same method as the primary safety endpoints.

Time to event endpoints will be analyzed using Kaplan-Meier approach and Cox regression will be used for comparing each fasinumab dose group and placebo by obtaining hazard ratios and their confidence intervals. The Cox regression model will include the fixed categorical effects of treatment-as-received and randomization strata.

Additionally, sensitivity analysis of the primary endpoint of incidence of destructive arthropathy as well as incidence of DA and JRs will be analyzed excluding patients who used NSAID during the trial.

Rescue Medication

The percentage of patients who use rescue medication between baseline and week 16 will be summarized by the treatment group for FAS-LTS.

Number of days patients used rescue medication during the treatment period (Day1 to Week 2, Week 2 to Week 4, Week 4 to Week 8, Week 8 to Week 12, Week 12 to Week 16...) will be summarized descriptively by treatment group. Weekly average amount of rescue medication use will be summarized by treatment group.

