5.1.8.2. Adverse Events of Special Interest

AESIs will be listed and summarized by treatment group based on the SAF-LTS. Differences in event rate for AESIs between fasinumab and placebo will be estimated using exact binomial confidence intervals.

Radiograph data related to AA including change from baseline in joint space width will be summarized by SAF over time. Within index type, Knee Society Score questionnaire or Harris Hip Score questionnaire results will be listed.

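### With no placebo events, the SAP's Wald interval for the rate difference ignores placebo person-time: 4 single-patient fasinumab events exclude zero, and 0 versus 0 gives zero width

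*SAP*

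**What the plan says.** SAP 4.5.1 defines the raw incidence rate as events divided by observation time, per 100 patient-years. Its list of primary safety variables includes "Incidence of destructive arthropathy events". Protocol 9.5.3 states that "The incidence rate differences and ratios between each fasinumab dose group and placebo will be computed", with 2-sided 95% intervals.

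SAP 5.1.7.1 gives two routes:

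- Placebo has events: the rate ratio comes from "Generalized Estimating Equations with a log-linked Poisson model via the PROC GENMOD procedure if there are events in the placebo group", and the difference interval from the same model.
- Placebo has none: the ratio is dropped and "confidence intervals for the incidence rate difference will be computed using Wald method". The variance form is not given, and no correction or alternative is named.

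SAP 5.1.8 carries the same method to exploratory incidence comparisons. It also plans a "sensitivity analysis of the primary endpoint of incidence of destructive arthropathy" that leaves out patients who used NSAIDs. Separately, SAP 5.1.8.2 says "Differences in event rate for AESIs between fasinumab and placebo will be estimated using exact binomial confidence intervals".

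**The concern.** The fallback is used only when placebo has no events, which is where an uncorrected Wald interval fails. The estimated placebo variance is then zero whether placebo contributed 100 or 1000 patient-years. The interval is too narrow, it leans towards signalling harm, and it shows complete certainty if neither arm has an event.

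Destructive arthropathy (DA) is the endpoint most exposed. Under Protocol 7.6.1.1, "adjudicated arthropathies will be evaluated to determine if they meet the criteria for destructive arthropathy", so DA is a subset of adjudicated arthropathy and cannot be more common. It is not listed separately among the adverse events of special interest (AESIs) in SAP 4.5.3, so no exact interval is assigned to DA in its own right. The repeat analysis without NSAID users has less person-time, which makes zero placebo events more likely.

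The opposite case is not covered either. If placebo has events and a fasinumab arm has none, SAP 5.1.7.1 still calls for the log-link Poisson model, which has no finite estimate for that arm.

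**Working it through.** **The plan's own figure.** SAP 2.2 works only an exact binomial example. Taking 52 events in 5250 patients, the Clopper-Pearson interval is 0.741% to 1.297%, which matches the stated 0.74% to 1.30%. There is no worked figure for the Wald fallback.

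**Inputs.**
- 2-sided 95% level, z = 1.96 (SAP 5.1.7.1).
- Rate = events / person-time (SAP 4.5.1).
- Allocation: "With approximately 1750 patients expected to be treated with placebo, a total of up to 7000 patients was planned to be randomized" (SAP 2.2), so 5250:1750 = 3:1 for all fasinumab against placebo. Amendment 8 is 3:3:1 (SAP 2.1): 3:1 for each 1 mg regimen, 6:1 for both pooled. Sub-study arms are 1:1.
- Assumptions: uncorrected variance, one event per patient. Person-years (PY) in the examples are assumed.

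**Wald interval.** With x events and T person-time (F fasinumab, P placebo):

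d ± 1.96·√(x_F/T_F² + x_P/T_P²). Setting x_P = 0 gives (x_F ± 1.96·√x_F)/T_F, and T_P has gone.

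The lower limit is positive when x_F > 1.96·√x_F, that is x_F > 3.84, so from 4 events. At T_F = 5250 PY, 3 events give -0.0075 to 0.1218 per 100 PY and 4 give 0.0015 to 0.1509. Zero events give 0 to 0.

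**Placebo follow-up has no effect.** For 5 events in 1800 PY against 0, Wald is 0.03 to 0.52 per 100 PY whether placebo has 100, 300 or 1000 PY. The score lower limits are -3.56, -1.00 and -0.11.

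**Fasinumab events needed to exclude zero, against 0 on placebo.** The exact conditional threshold is the smallest x with (k/(k+1))^x ≤ 0.025, for allocation k:1.

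| Ratio | Wald | Score | Exact conditional |
|---|---|---|---|
| 1:1 | 4 | 4 | 6 (0.0156) |
| 3:1 | 4 | 12 | 13 (0.0238) |
| 6:1 | 4 | 24 | 24 (0.0247) |

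For 4 against 0 at 3:1, the exact one-sided p is 0.75⁴ = 0.32.

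**False exclusion with equal true rates.** With m expected placebo events, P(no placebo event and at least 4 on fasinumab) = e^(-m) · P(Poisson(k·m) ≥ 4). The nominal figure is 2.5% per side.

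| m | 0.25 | 0.5 | 1 | 1.5 | 2 | 3 | 4 | Peak |
|---|---|---|---|---|---|---|---|---|
| 3:1 | 0.6% | 4.0% | 13.0% | 14.7% | 11.5% | 4.9% | 1.8% | 14.9% (m = 1.35) |
| 6:1 | 5.1% | 21.4% | 31.2% | 21.8% | 13.5% | 5.0% | 1.8% | 32.0% (m = 0.87) |

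At 1:1 the peak is 2.0% (m = 2.32).

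**Examples at 3:1 (PY assumed), per 100 PY.**
- 5 in 900 PY against 0 in 300 PY: Wald 0.56 (0.07 to 1.04); score -0.72 to 1.30; exact one-sided p 0.75⁵ = 0.24.
- 5 in 3000 PY against 0 in 1000 PY: Wald 0.17 (0.02 to 0.31); score -0.22 to 0.39; same p.
- 0 in 900 PY against 0 in 300 PY: Wald 0 to 0; score -1.28 to 0.43.

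**True rates at which this matters.** If all 1750 planned placebo patients reach week 72, placebo time is 1750 × 505 days, about 2400 PY. The range m = 0.5 to 3 is then about 0.02 to 0.12 per 100 PY. At an assumed 300 placebo PY it is 0.17 to 1.0 per 100 PY.

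**The case against.** The algebra is not in dispute; the size and importance are.

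- **Ratios.** The planned comparison is each dose against placebo in the pooled long-term safety set. The 3:1 overall ratio combines all fasinumab doses, and the SAP specifies no rate analysis restricted to amendment 8, so 6:1 is an upper bound. Each 1 mg arm and placebo also include about 200 sub-study patients at 1:1. Assuming 300 amendment 8 placebo patients, the per-dose ratio is (200 + 900):(200 + 300) = 2.2:1, with a peak of 9.4%. At 2:1 the peak is 8.1%, and at 1.5:1 it is 4.8%. Earlier placebo patients, if pooled, lower the ratio further. This stands: 14.9% is near the top for a 1 mg dose, but an excess remains.
- **Variance form.** Events can recur within a patient: Protocol 1.1 reports 26 adjudicated arthropathy events in 24 patients. Under a robust variance, 4 events split 2+1+1 no longer exclude zero. This stands for the threshold. Placebo person-time still drops out, and 0 against 0 still has zero width.
- **Other outputs.** Exact binomial intervals cover the AESIs, including adjudicated arthropathy, which contains every DA case. Time to DA is also analysed, and arm-specific rates are shown, so a reader will see 4 against 0. This limits the harm but does not correct the person-time interval. The exact intervals concern proportions and do not replace the fallback.
- **Purpose.** The objective is descriptive, no decision rule applies, and an interval that wrongly excludes zero errs towards caution. That limits the severity, but describing safety is the primary objective, and these intervals state its precision.
- **Frequency.** The documents give no DA rate, so whether the fallback will be used is unknown.

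**Conclusion.** The concern holds. The SAP prescribes Wald in the one situation where the estimated placebo variance is zero. Loss of placebo person-time and the zero-width interval at 0 against 0 hold for a model-based or robust uncorrected Wald variance. The 4-event threshold also needs one event per patient.

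The chance of wrongly excluding zero through this route peaks at 14.9% at 3:1 and at about 5 to 9% for plausible pooled per-dose ratios. It reaches 32.0% only if both 1 mg regimens are pooled within amendment 8, and there is no excess at 1:1. At 3:1 the excess lies between about 0.5 and 3 expected placebo events; above about 4 the fallback is rarely reached. The result would be a misleading interval for a primary safety variable, not a wrong test decision. It should be fixed before the safety analysis.

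**What to change.** In SAP 5.1.7.1, replace the Wald fallback with a score-type (Miettinen-Nurminen) or exact interval for the difference of two Poisson rates. Apply it whenever either arm has no events, so that a zero in a fasinumab arm and zeros in both arms are covered too. It would be useful to add which interval is the main one for AESIs: this one or the exact binomial interval of SAP 5.1.8.2.

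The cost is one or two sentences and a standard routine. When an arm has no events, the interval will be wider, will not be adjusted for the randomization strata, and will assume independent events, one per patient.

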In 2012, non-clinical studies of the sponsors of other anti-NGF monoclonal antibodies identified adverse changes in the sympathetic nervous system of mature animals of several species (rat and non-human primate). These effects included a reversible decrease in neuron volume. To date, no statistically significant or consistent effects of fasinumab on the sympathetic nervous system have been detected in animal studies with up to 6-months of treatment. Based on the potential risk of sympathetic nervous system toxicity identified in non-clinical studies of other anti-NGF monoclonal antibodies, a risk-mitigation approach is being implemented for all fasinumab studies, as outlined in Section 7.6.1.2.

In the phase 2/3 study of fasinumab in patients with pain due to OA of the knee or hip (R475-PN-1227), 26 AA events occurred in 24 patients. There was an increase in AA events that appeared to be related to greater fasinumab dose. Although these events were milder than the severe DA events presented at the 2012 FDA Arthritis Advisory Committee, in consideration of the lack of an observed dose response for efficacy in OA, the benefit-risk ratio was deemed unfavorable for the fasinumab 6 mg Q4W and 9 mg Q4W doses in patients with OA, in comparison to the other fasinumab doses that were studied, (ie, 1 mg Q4W and 3 mg Q4W). Accordingly, 6 mg Q4W and 9 mg Q4W were removed from the present study in an amendment issued in June 2016. The dose regimens that were being evaluated in the phase 3 studies for OA pain in the knee or hip included 1 mg Q8W, 1 mg Q4W, 3 mg Q4W, and 6 mg Q8W. In April 2018, the independent Data Monitoring Committee (DMC) recommended discontinuing 6 mg Q8W and 3 mg Q4W (expected to have similar exposure to 6 mg Q8W) based on a review of unblinded data in the present study. Subsequently, a small Regeneron team reviewed the data and agreed with this recommendation. The DMC noted imbalances in clinically relevant adverse events including time to total joint replacement, peripheral edema, arthralgia and a trend towards early fractures. The phase 3 program for OA pain in the hip or knee will continue to evaluate fasinumab 1 mg with the highest dose regimen of 1 mg Q4W, which is supported by the independent DMC as having a favorable benefit-risk profile.

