5. STATISTICAL METHODS

For continuous variables, descriptive statistics will include the following: the number of patients reflected in the calculation (n), mean, median, standard deviation (SD), minimum, maximum, and the first and third quartiles (Q1 and Q3).

For categorical or ordinal data, frequencies and percentages will be displayed for each category.

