
Laboratory Safety Variables below LLOQ or above ULOQ

For central laboratory data below the lower limit of quantification (LLOQ), half of the lower limit value (i.e., LLOQ/2) will be used for quantitative analyses.

Missing laboratory, ECG, vital sign, physical exam, neurological exam

No imputations for missing laboratory data, ECG data, vital sign data, physical examination, or neurological examination data will be made.

Handling of Potentially Clinically Significant Abnormalities

If a patient has a missing baseline value they will be grouped in the category “normal/missing at baseline”.

For PCSAs with 2 conditions, one based on a change from baseline value and the other on a threshold value or a normal range, with the first condition being missing, the PCSA will be based only on the second condition.

For a PCSA defined on a threshold and/or a normal range, this PCSA will be derived using this threshold if the normal range is missing; eg, for eosinophils the PCSA is >0.5 GIGA/L or >ULN if ULN \geq 0.5 GIGA/L. When ULN is missing, the value 0.5 should be used.

Measurements flagged as invalid by the laboratory will not be summarized or taken into account in the computation of PCSA values.

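### Index-joint space width, a primary safety variable in the SAP, has no between-arm estimate and no rule for replaced joints, so its by-visit tables may understate structural loss

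*SAP*

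**What the plan says.** SAP 4.5.1 includes among the primary safety variables "Change from baseline in minimum joint space width of the index joint (knee, hip"). Protocol 8.2 does not name JSW in the primary endpoint.

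Three places describe the JSW analysis, and all are descriptive:

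- SAP 5.1.7.1, for continuous variables: "Continuous variables will be summarized by baseline and change from baseline to each scheduled assessment time with descriptive statistics". The Poisson model with strata, rate ratios, rate differences and 95% CIs in the same section applies to incidence rates only.
- SAP 5.1.8.2: "Radiograph data related to AA including change from baseline in joint space width will be summarized by SAF over time".
- Protocol 9.5.3: "Change from baseline in joint space width of the index knee or hip will be summarized by treatment group".

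SAP 5 defines the descriptive set as n, mean, median, SD, minimum, maximum and both quartiles.

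SAP 5.1.8 adds no method. It says "The exploratory safety variables comparing change from baseline scores of each fasinumab dose group and placebo will be analyzed using the same method". This points back to 5.1.7.1, which contains no method for comparing change scores.

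On missing values, SAP 6.3 says "No imputations for missing laboratory data, ECG data, vital sign data, physical examination, or neurological examination data will be made". Radiographic measurements are not in that list, and nothing else in the SAP covers them.

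Radiographs are scheduled at screening and weeks 24, 52, 60 and 72, at the visit before joint replacement (JR), and 4 and 20 weeks after JR (Protocol Tables 1, 2, 4 and 5). SAP 6.4 and 6.5 map an assessment without a nominal visit to one window, and where several fall in a window keep the one closest to the target day.

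**The concern.** JSW is the only continuous measure of structural change among the variables that SAP 4.5.1 names. Once the index joint is replaced it has no native JSW, so each later row describes only patients whose joint has survived to that visit. If joints that lose more space are more often replaced, each row is a selected sample. If replacement is also more frequent on fasinumab, the selection is stronger in that arm.

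The documents give some reason to expect this. Protocol 1.2 says that some fasinumab patients with joint damage were more likely to undergo JR. Protocol 1.1 records, for the higher doses, "The DMC noted imbalances in clinically relevant adverse events including time to total joint replacement".

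What is at stake is how the JSW table is read. Similar by-visit changes in the arms could be taken as structural reassurance when part of the loss has left the table. With no contrast or interval, the reader also cannot tell how large a difference the data exclude.

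**Working it through.** **Stated figures.** The documents give no SD, expected loss or precision for JSW, and no JR rate by arm. The one safety precision statement is for incidence (SAP Table 1). It reproduces: an exact binomial interval for 52/5250 is 0.741% to 1.297%, against the stated 0.74% to 1.30%. It says nothing about JSW.

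**Where the pre-operative film goes.** By the SAP 6.4 windows, visits with a scheduled radiograph cover these days, with week 72 cut at its target day 505:

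- week 24, days 156 to 183: 28
- week 52, days 352 to 393: 42
- week 60, days 394 to 463: 70
- week 72, days 464 to 505: 42

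The total is 182 of 504 post-baseline days, or 36%. If pre-operative films were spread evenly over time (an assumption), about 64% would fall in windows with no scheduled radiograph. In the other windows, a scheduled film nearer the target day would displace the pre-operative one. In neither case does the value reach a later row.

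**Size in a row after the replacements.** Let p be the proportion of index joints replaced, L_R their mean loss and L_U the mean loss in the others.

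- Mean loss, all patients: p·L_R + (1 − p)·L_U
- Mean loss, patients still in the row: L_U
- Understatement: p·(L_R − L_U) = p·e, where e is the excess loss in replaced joints
- Bias in the arm difference, with the same e in both arms: (p_F − p_P)·e

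All inputs below are assumed. Entries are the bias in the difference, in mm.

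| JR placebo vs fasinumab | e = 0.5 mm | e = 1.0 mm | e = 2.0 mm |
|---|---|---|---|
| 1% vs 2% | 0.005 | 0.010 | 0.020 |
| 2% vs 4% | 0.010 | 0.020 | 0.040 |
| 3% vs 6% | 0.015 | 0.030 | 0.060 |
| 5% vs 10% | 0.025 | 0.050 | 0.100 |
| 3% vs 3% | 0 | 0 | 0 |

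**Simulation.** Assumed: SD 0.5 mm, mean change −0.10 mm on placebo and −0.20 mm on fasinumab, and JR log-odds linear in JSW loss, with JR probability 2% and 5% at zero change. The true difference is −0.10 mm.

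| Log-odds slope per SD of loss | JR placebo vs fasinumab | Difference among unreplaced joints |
|---|---|---|
| 0 | 2.0% vs 5.0% | −0.10 |
| 0.5 | 2.5% vs 6.7% | −0.09 |
| 1.0 | 3.8% vs 10.2% | −0.07 |
| 1.5 | 6.1% vs 15.2% | −0.05 |

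With mean change −0.10 mm in both arms instead, the three non-zero slopes give differences of about +0.01, +0.02 and +0.035 mm, a spurious advantage for fasinumab.

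**The case against.** The strongest reply is that these patients are not lost to the safety analysis. SAP 4.5.1 also lists incidence of JR, adjudicated arthropathy and destructive arthropathy. SAP 5.1.7.1 gives incidence rates a stratified model with intervals, SAP 5.1.8 adds Kaplan-Meier and Cox analyses of time to JR decision and to each arthropathy, and SAP 5.1.8.1 lists every JR. The study objective is to describe safety, so a descriptive JSW table contradicts nothing. All of this stands, and it limits the point to what the JSW table can show.

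Four stronger readings are tempting, and the documents do not support them:

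- *The plan conceals structural harm.* It does not; harm that leads to JR or arthropathy is counted elsewhere, with intervals.
- *Only means are shown.* Quartiles, extremes and n are planned too. A falling n signals attrition but not its cause, and no statistic in a row recovers a patient who is absent from it.
- *The worst joints are the ones that leave, more so on fasinumab.* Protocol 1.2 also reports higher JR risk in fasinumab patients without joint damage. Protocol 1.3.2 ties the imbalance seen by the DMC to the discontinued 6 mg regimens. No JR difference is shown for 1 mg.
- *The whole arm difference would vanish.* Assume a loss of 2.0 mm in replaced joints, 0.1 mm in all others, and JR of 4% versus 2%. The true means are 0.04 × 2.0 + 0.96 × 0.1 = 0.176 mm and 0.02 × 2.0 + 0.98 × 0.1 = 0.138 mm, and the 0.038 mm difference disappears among unreplaced joints. But that follows from placing the entire drug effect in the replaced joints.

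The SAP also never states that patients are dropped after JR. It is silent, and films continue after surgery, so even the handling of a film showing a prosthesis in the index joint is undefined.

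**Conclusion.** The concern holds as a gap in specification with a conditional bias. JSW is a primary safety variable with no between-arm estimate, no interval, no adjustment and no rule after index-joint replacement. By-visit summaries may then understate loss and the arm difference, provided that JR depends on JSW loss and that JR rates, or the excess loss in replaced joints, differ by arm. The first condition has partial support in the protocol. The second was reported only for regimens since stopped, although patients from those arms remain in the LTS safety set.

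Under the assumed ranges the bias in the difference is 0.005 to 0.10 mm, and in the simulation up to about half of a true 0.10 mm difference. It is zero if JR is unrelated to JSW loss. Rows before the replacements are unaffected. The conclusions on JR and arthropathy do not depend on this; the risk is a JSW table that is falsely reassuring when read alone.

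**What to change.** In SAP 5.1.7.1, for knees and hips separately:

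1. Estimate fasinumab minus placebo in change in index-joint minimum JSW, with 95% CI, from a repeated-measures model adjusted for baseline JSW and the randomization strata (K-L category, region). State that only native-joint films enter. The sub-study already uses a model of this kind (SAP 5.2.7.1.1).
2. Add a supportive summary of each patient's last or worst native-joint change, including the pre-operative film where one of readable and comparable quality exists. This is needed because the by-visit model would still miss films outside the scheduled radiograph windows.
3. Show the cumulative number of index joints replaced beside each visit row, by arm.

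The cost is SAP text and a few tables from data already being collected. There are three limits. A worst-change summary is noisier than a visit mean. Some pre-operative films will be missing or not in the standard view, since Protocol 6.2.11 asks for them only where possible and 6.3.4.10 accepts standard-of-care images. After JR the model estimate refers to a hypothetical unreplaced joint, so it should be presented beside JR incidence.
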